6.2. Visit 2 - Follow-up Visit (28 to 42 Days After Visit 1)

- Review the subject's e-diary data and collect the e-diary. Collect stop dates of any e-diary events ongoing on the last day that the e-diary was completed and record stop dates in the CRF.
- Determine whether any AEs (including SAEs) have occurred since the last study visit and record them on the CRF (see [Section 8](#)).
- Collect and record any follow-up information on previously documented AEs and SAEs and record their end dates or confirm that they are still continuing.
- Record any nonstudy vaccinations.
- Confirm use of appropriate contraceptives (if appropriate).
- Complete the source documents and the CRFs.

6.3. Unscheduled Reactogenicity Visit

If the subject's parent(s)/legal guardian(s)/caregiver(s) report(s) redness or swelling at the injection site measuring >14 measuring device units (>7.0 cm), a contact **must** occur as soon as possible between the subject's parent(s)/legal guardian(s)/caregiver(s) and the investigator, or a medically qualified member of the study site staff, to assess if an unscheduled visit is required.

A site visit must be scheduled as soon as possible to assess the extent of the reaction unless:

- The subject is unable to attend the unscheduled visit, or
- The reaction is no longer present at the time of the contact, or
- An incorrect value was entered into the e-diary (confirmation of an e-diary data entry error).

This contact will be recorded in the CRF and in the subject's source documentation.

If the subject is unable to attend the unscheduled visit, any ongoing reactions must be assessed at the next scheduled visit.

The reaction(s) should be assessed by the investigator or a medically qualified member of the site staff such as a study physician or a study nurse, as applicable to the investigator's local practice, who will:

- Measure axillary temperature.
- Measure the minimum and maximum diameter of the redness or swelling in centimeters.
- Assess pain at the injection site (tenderness) in accordance with the criteria provided in [Section 7.3.1](#).
- Complete the CRF.
- If applicable, remind the subject's parent(s)/legal guardian(s)/caregiver(s) to enter an end date of the reaction in the e-diary.

6.4. Subject Withdrawal

Subjects may withdraw from the study at any time at their own request, or at the request of their parent(s)/legal guardian(s), or they may be withdrawn at any time at the discretion of the investigator or sponsor for safety (see also the Withdrawal From the Study Due to Adverse Events section) or behavioral reasons, or the inability of the subject to comply with the protocol-required schedule of study visits or procedures at a given study site.

If a subject does not return for a scheduled visit, every effort should be made to contact the subject. All attempts to contact the subject and information received during contact attempts must be documented in the subject's medical record. In any circumstance, every effort should be made to document subject outcome, if possible. The investigator should inquire about the reason for withdrawal and request that the subject return for a final visit, if applicable, and follow up with the subject regarding any unresolved AEs.

If the subject withdraws from the study, and also withdraws consent for disclosure of future information, no further evaluations should be performed, and no additional data should be collected. The sponsor may retain and continue to use any data collected before such withdrawal of consent.

Subjects who withdraw from the study will not be replaced.

7. ASSESSMENTS

Every effort should be made to ensure that the protocol-required tests and procedures are completed as described. However, it is anticipated that from time to time there may be circumstances outside of the control of the investigator that may make it unfeasible to perform the test. In these cases the investigator will take all steps necessary to ensure the safety and well-being of the subject. When a protocol-required test cannot be performed, the investigator will document the reason for this and any corrective and preventive actions that he or she has taken to ensure that normal processes are adhered to as soon as possible. The study team will be informed of these incidents in a timely manner.

7.1. Pregnancy Testing

For female subjects of childbearing potential, a urine pregnancy test, with sensitivity of at least 25 mIU/mL, will be performed immediately before administration of the vaccine dose. A negative pregnancy test result is required before the subject may receive the investigational product. Pregnancy tests may also be repeated if requested by institutional review boards (IRBs)/ethics committees (ECs) or if required by local regulations. In the case of a positive confirmed pregnancy, the subject will be withdrawn from administration of investigational product.

7.2. Safety Assessments

Safety parameters will be assessed as described in the Schedule of Activities and below.

A medical history and physical examination, including measurement of vital signs, will be performed on all subjects at Visit 1. Significant medical history and observations from the physical examination will be documented in the CRF.

The safety parameters include e-diary reports of local reactions at the 13vPnC injection site and systemic events that occur in the 7 days after investigational product administration. These prospectively collected occurrences of local reactions and systemic events are graded as described in [Section 7.3](#).

Acute reactions within the first 20 minutes after investigational product administration will be assessed and documented in the AE CRF.

In addition, AEs and SAEs are collected, recorded, and reported as defined in [Section 8](#).

7.3. Electronic Diary

The subject's parent(s)/legal guardian(s)/caregiver(s) will be issued an e-diary and will be asked to monitor and record the subject's local reactions and systemic events for 7 days after 13vPnC vaccination. The e-diary allows recording of these assessments only within a fixed time window, thus providing the accurate representation of the subject's experience at that time. Local reactions and systemic events reported on the e-diary will be transferred electronically to the e-diary vendor (a trusted third party), where they will be available for review by investigators at all times via an internet-based portal. At intervals agreed upon between the vendor and Pfizer, these data will be transferred electronically into Pfizer's database for analysis and reporting. The e-diary data do not need to be reported by the investigator in the CRF.

Investigators will be required to review the e-diary data online at frequent intervals to evaluate the subject's caregiver e-diary completion compliance and as part of the ongoing safety review.

7.3.1. Local Reactions

Local reactions (redness, swelling, and pain) at the 13vPnC injection site will be monitored daily for 7 days (Day 1 to Day 7) after each vaccination. An end date will be captured for all reactions either via the e-diary or CRF as applicable.

Redness and swelling will be measured and recorded in measuring device units and then categorized during analysis as mild, moderate, or severe based on the grading scale in [Table 1](#) below. Measuring device units can be converted to centimeters according to the following scale: 1 measuring device unit = 0.5 cm.

Pain at the vaccine injection site will be assessed by the subject's parent(s)/legal guardian(s)/caregiver(s) as mild, moderate, or severe according to the grading scale in [Table 1](#) below.

If a subject experiences redness or swelling at the injection site measuring greater than 7 cm (>14 measuring device units), an unscheduled visit should take place to assess the reaction.

If a local reaction persists beyond the end of the e-diary period, the subject's parent(s)/legal guardian(s)/caregiver(s) will be requested to report that information and/or any new AEs that develop to the investigator. The investigator will enter this additional information in the subject's source notes and CRF.

Table 1. Grading Scale for Local Reactions

	Mild Grade 1	Moderate Grade 2	Severe Grade 3
Redness	1 to 4 measuring device units = 0.5 to 2.0 cm	5 to 14 measuring device units = 2.5 to 7.0 cm	>14 measuring device units = >7 cm
Swelling	1 to 4 measuring device units = 0.5 to 2.0 cm	5 to 14 measuring device units = 2.5 to 7.0 cm	>14 measuring device units = >7 cm
Pain at injection site (Tenderness)	Does not interfere with activity	Interferes with activity	Prevents daily activity

7.3.2. Systemic Events

Following vaccination at Visit 1 (Day 1 through Day 7, where Day 1 is the day of vaccination), the subject’s parent(s)/legal guardian(s)/caregiver(s) will be asked to assess fatigue, headache, vomiting, diarrhea, muscle pain, and joint pain and to record the symptoms in the e-diary in the evening. The symptoms will be assessed as mild, moderate, or severe according to the grading scale in Table 2 below.

If a systemic event persists beyond the end of the e-diary period, the subject’s parent(s)/legal guardian(s)/caregiver(s) will be requested to report that information and/or any new AEs that develop to the investigator. The investigator will enter this additional information in the CRF.

Table 2. Grading Scale for Systemic Events

	Mild Grade 1	Moderate Grade 2	Severe Grade 3
Fatigue (= tiredness in diaries)	Does not interfere with activity	Some interference with activity	Prevents daily routine activity
Headache	Does not interfere with activity	Some interference with activity	Prevents daily routine activity
Vomiting	1 to 2 times in 24 hours	More than 2 times in 24 hours	Requires intravenous hydration
Diarrhea	2 to 3 loose stools in 24 hours	4 to 5 loose stools in 24 hours	6 or more loose stools in 24 hours
Muscle pain	Does not interfere with activity	Some interference with activity	Prevents daily routine activity
Joint pain	Does not interfere with activity	Some interference with activity	Prevents daily routine activity

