7.3.3. Fever

A digital thermometer will be provided with instructions on how to measure the subject's temperature at home. Temperature will be collected in the evening daily for 7 days following vaccination (Day 1 through Day 7, where Day 1 is the day of vaccination) and at any time during the 7 days after Visit 1 that fever is suspected. Fever is defined as a temperature of $\geq 100.4^{\circ}\text{F}$ ($\geq 38.0^{\circ}\text{C}$). The highest temperature for each day will be recorded in the e-diary.

In the event of a fever on Day 7, temperature will be measured daily until fever has resolved (1 day of temperature less than 100.4°F [38.0°C]) in order to collect a stop date in the CRF.

Temperature will be measured and recorded to 1 decimal place and then grouped into ranges for the analysis according to Table 3 below:

Table 3. Ranges for Fever (All Subjects)

Fever	38.0°C to 38.4°C	38.5°C to 38.9°C	39.0°C to 40.0°C	>40.0°C
	100.4°F to 101.1°F	101.2°F to 102.0°F	102.1°F to 104.0°F	>104.0°F

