3.4.1.1. Local Reactions

Local reactions (redness, swelling, and pain) at the 13vPnC injection site will be monitored daily for 7 days (Day 1 to Day 7) after each vaccination. An end date will be captured for all reactions either via the e-diary or in the case report form (CRF) as applicable.

Redness and swelling will be measured and recorded in measuring device units for 7 days following vaccination (Day 1 to 7), and then categorized using the scale shown in Table 2 below. The measurements will then be recorded in the e-diary.

A measuring device will be given to the subject’s parent(s)/legal guardian(s)/caregiver(s) with instructions for measuring any redness or swelling at the injection site. Each measuring device unit is equivalent to 0.5 cm. The subject’s parent(s)/legal guardian(s)/caregiver(s) will be asked to measure and to report the largest diameters of a local reaction. In case a measurement is between 2 values, the higher value should be reported. At the time of entry into the e-diary, the subject’s parent(s)/legal guardian(s)/caregiver(s) should record the maximum severity of the reaction since the previous entry into the e-diary.

Pain at the vaccine injection site will be assessed by the subject’s parent(s)/legal guardian(s)/caregiver(s) as mild, moderate, or severe according to the grading scale in Table 2 below.

Table 2. Grading Scale for Local Reactions

| | Mild Grade 1 | Moderate Grade 2 | Severe Grade 3 |
|-------------------------------------|--|---|---|
| Redness | 1 to 4 measuring device units = 0.5 to 2.0 cm | 5 to 14 measuring device units = 2.5 to 7.0 cm | >14 measuring device units = >7 cm |
| Swelling | 1 to 4 measuring device units = 0.5 to 2.0 cm | 5 to 14 measuring device units = 2.5 to 7.0 cm | >14 measuring device units = >7 cm |
| Pain at injection site (tenderness) | Does not interfere with activity | Interferes with activity | Prevents daily activity |

If a local reaction persists beyond the end of the e-diary period, the subject’s parent(s)/legal guardian(s)/caregiver(s) will be requested to report that information and/or any new AEs that develop to the investigator. The investigator will enter this additional information in the subject’s source notes and CRF.

For events that were ongoing on the last day that the e-diary was completed, the end date will be collected in the CRF.

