3.4.1.2. Systemic Events, Including Fever

The systemic events reported in the e-diary following vaccination are fatigue, headache, vomiting, diarrhea, muscle pain, and joint pain. These will be recorded as present or absent. Fever is also included as a systemic event.

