3.4.1.2.2. Systemic Events

The presence of systemic events (fatigue, headache, vomiting, diarrhea, muscle pain, and joint pain) will be recorded in the e-diary daily for 7 days (Day 1 through Day 7, where Day 1 is the day of vaccination) after vaccination, using the grading scale in Table 7 below.

If a systemic event persists beyond the end of the e-diary period, the subject’s parent(s)/legal guardian(s)/caregiver(s) will be requested to report that information and/or any new AEs that develop to the investigator. The investigator will enter this additional information in the CRF.

Table 7. Grading Scale for Systemic Events

| | Mild Grade 1 | Moderate Grade 2 | Severe Grade 3 |
|-------------------------------------|----------------------------------|---------------------------------|------------------------------------|
| Fatigue (= tiredness in diaries) | Does not interfere with activity | Some interference with activity | Prevents daily routine activity |
| Headache | Does not interfere with activity | Some interference with activity | Prevents daily routine activity |
| Vomiting | 1 to 2 times in 24 hours | More than 2 times in 24 hours | Requires intravenous hydration |
| Diarrhea | 2 to 3 loose stools in 24 hours | 4 to 5 loose stools in 24 hours | 6 or more loose stools in 24 hours |
| Muscle pain | Does not interfere with activity | Some interference with activity | Prevents daily routine activity |
| Joint pain | Does not interfere with activity | Some interference with activity | Prevents daily routine activity |

For fatigue (synonymous with tiredness in the e-diaries), headache, muscle pain, and joint pain on each day, an indicator variable will be created for them for each day separately, using the following algorithm:

- = ●, if fatigue, headache, muscle pain, or joint pain is missing
- = 0 (none), if no fatigue, headache, muscle pain, or joint pain
- = 1 (mild), if does not interfere with activity
- = 2 (moderate), if some interference with activity
- = 3 (severe), if prevents daily routine activity

For vomiting on each day, an indicator variable will be created for each day using the following algorithm:

- = ●, if vomiting is missing
- = 0 (none), if no vomiting
- = 1 (mild), if 1 to 2 times in 24 hours
- = 2 (moderate), if more than 2 times in 24 hours
- = 3 (severe), if requires intravenous hydration

For diarrhea on each day, an indicator variable will be created for each day using the following algorithm:

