6.3.2. Reactogenicity Data

The derived endpoints ([Section 3.4.1](#)) for each local reaction and systemic event will be summarized.

The presence and maximum severity of each local reaction and systemic event, including fever, and any event within 7 days following vaccination with 13vPnC, will be summarized by proportions of subjects with the associated 95% Clopper-Pearson CIs.

The presence of each local reaction and systemic event, and any local reaction and systemic event, including fever, on each day and any day of Day 1 to Day 7 following vaccination with 13vPnC, will also be summarized by proportions of subjects with associated Clopper-Pearson CIs.

For each local reaction and systemic event, including fever, descriptive summary statistics of the maximum duration of each event will be provided. The maximum duration of each event for each subject will be calculated as the last day with the event minus the first day with the event + 1, ignoring any intervening days without the indicated event.

For the onset of each local reaction and systemic event, including fever, descriptive summary statistics will be provided.

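### Are fatigue, headache, muscle pain and joint pain under-counted because no recall period is stated for the evening diary entry?

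*Protocol*

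**What the plan says.** Ten reactions and events are solicited by e-diary for 7 days: three local (redness, swelling, pain) and seven systemic, counting fever (SAP 3.4.1). For six of them the period behind each entry is stated.

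- Redness, swelling and pain: SAP 3.4.1.1 says the caregiver "should record the maximum severity of the reaction since the previous entry into the e-diary".
- Fever: Protocol 7.3.3 says "The highest temperature for each day will be recorded in the e-diary".
- Vomiting and diarrhea: the grading table in Protocol 7.3.2, repeated in SAP 3.4.1.2.2, uses 24-hour counts, for example "1 to 2 times in 24 hours" for mild vomiting.

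For fatigue, headache, muscle pain and joint pain, Protocol 7.3.2 asks the caregiver to assess them and "to record the symptoms in the e-diary in the evening". SAP 3.4.1.2 adds "These will be recorded as present or absent", and SAP 3.4.1.2.2 says their presence "will be recorded in the e-diary daily for 7 days". Their grades describe interference with activity and name no look-back period. Protocol 7.3 says the device allows "recording of these assessments only within a fixed time window, thus providing the accurate representation of the subject's experience at that time".

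SAP 6.3.2 then summarizes "The presence and maximum severity of each local reaction and systemic event, including fever, and any event within 7 days following vaccination", as well as presence on each day, duration and onset.

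**The concern.** Symptom present this evening and symptom present at any time today are different endpoints. The closing phrase of the e-diary sentence in Protocol 7.3 can be taken to mean the first. On that reading, the 7-day maximum for these four symptoms would be the worst of seven evening states, shown in the same tables as events measured over a full day.

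The error would run one way. A headache that came and went before evening would be scored absent, and nothing would be scored present that was not. The exact confidence interval does not allow for this. Because entries are accepted only in a fixed window, the score could not be repaired later. Medication is permitted but not documented (Protocol 5.5.2), so a treated symptom would leave no trace in the diary.

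The stakes are not trivial. Systemic events within 7 days are a primary endpoint, and the earlier India study used no e-diary (Protocol 1.2), so these rates are much of what the present study adds.

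**Working it through.** **What is missing.** Period stated: 3 local reactions + fever + vomiting + diarrhea = 6 of 10. Not stated: 10 − 6 = 4. Nothing elsewhere supplies it. SAP 3.4.1.2.2 borrows the local-reaction algorithms only for the any-day and any-event derivations, and the maximum severity in SAP 6.3.2 is a summary across days, not an instruction to the caregiver.

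**Which reading fits.** Set against the rest of the text, the momentary reading does poorly.

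1. In Protocol 7.3.2 the evening is attached to recording. The assessing runs over Day 1 through Day 7.
2. The same instruction covers vomiting and diarrhea, graded over 24 hours. The evening entry therefore already looks back for two of its six symptoms.
3. The severe grade for all four symptoms is that the daily routine is prevented, which is hard to rate as a state at one moment.
4. Protocol 7.3 asks caregivers to monitor as well as record, SAP 3.4.1.2.2 speaks of daily recording, and Protocol 9.2 counts events on any day of the 7-day period.
5. The sentence containing "recording of these assessments only within a fixed time window, thus providing the accurate representation of the subject's experience at that time" covers local reactions and systemic events alike. Taken as momentary, it would contradict the fever rule, the 24-hour counts and the SAP rule for local reactions. Taken as a bar on late back-filling, it contradicts nothing.

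**Size, if the momentary reading were true.** The plan gives no figure for this, so there is none to reproduce; every input below except N = 100 (Protocol 3.3) and the exact interval (SAP 5.2.1) is an assumption.

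Let p be the true any-day rate, k the number of days with the symptom, and q the chance that it is gone by the entry on a given day, with days independent. A subject is lost only if missed on all k days, so

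observed rate = p(1 − q^k).

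| p | q | k = 1 | k = 2 |
|---|---|---|---|
| 20% | 0.10 | 0.20 × 0.90 = 18.0% | 0.20 × 0.99 = 19.8% |
| 20% | 0.25 | 0.20 × 0.75 = 15.0% | 0.20 × 0.9375 = 18.8% |
| 20% | 0.50 | 0.20 × 0.50 = 10.0% | 0.20 × 0.75 = 15.0% |
| 10% | 0.10 | 9.0% | 9.9% |
| 10% | 0.25 | 7.5% | 9.4% |
| 10% | 0.50 | 5.0% | 7.5% |

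Exact 95% intervals at N = 100 are 12.7% to 29.2% for 20/100 and 4.9% to 17.6% for 10/100. In the p = 20% rows only 10.0% lies outside the first. In the p = 10% rows nothing lies outside the second; 5.0% is just inside.

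With q = 0, which is what a whole-day question gives, the observed rate equals p.

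**The case for a change.** The strongest case is that a primary endpoint should not depend on inference. Six events have a rule and four do not, so the contrast may be taken as meaningful, and the wording about experience at the time of entry is in the protocol. A bias that goes only downward is also poorly judged by whether one interval still contains the truth. Coverage is a sharper measure: sum the binomial probabilities, with n = 100 and rate p(1 − m), over all counts whose exact interval contains p, where m is the share of affected subjects missed on every day.

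| m | p = 20% | p = 40% |
|---|---|---|
| 0 | 96.7% | 95.8% |
| 10% | 95.6% | 87.3% |
| 30% | 75.9% | 28.5% |
| 50% | 29.7% | 0.6% |

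The omission stands, and so does the direction of any bias. It is also fair that each-day, duration and severity summaries are more exposed than the any-day rate, which loses only subjects missed at every entry.

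The inference that a bias exists does not stand. At p = 20%, a 10% miss does little; serious loss of coverage needs around 30% or more of affected subjects to be missed on every day, and nothing in the documents supports such a rate or shows that the diary asks for the state at entry. The diary screens and caregiver instructions, which would settle it, are not among the documents.

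The medication point adds little: the mechanism works with or without treatment, and a medication record would not restore a diary score. Some missed symptoms could still surface as adverse events through the Visit 2 questioning (Protocol 6.2 and 8.1.2), though not in the diary endpoint.

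Nor is there one obvious sentence to add. Carrying over the local-reaction rule would make an entry span more than a day after a missed evening, which the SAP's missing-day rules expect to happen, and would differ from the 24-hour basis for vomiting and diarrhea in the same entry. The choice between the day, 24 hours and the time since the last entry is largely preference.

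**Conclusion.** The plan leaves the recall period unstated for four of ten solicited events, but the surrounding text points to the whole day and the programmed diary question fixes it in practice. This is a gap that analysts fill sensibly: they report the four symptoms according to the question the caregivers answered. Stating that period in the protocol and SAP would document the measurement without altering the data, the analysis population, the derivations or the intervals.

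The size is zero if the diary asks about the whole day. If it asked only about the moment of entry, the illustrative fall in an any-day rate of 20% would run from 0.2 percentage points (q = 0.10, two days) to 10 points (q = 0.50, one day), on inputs that the documents do not provide. The conclusion rests on the whole-day reading being the one programmed; the documents favor it but do not prove it. No change to the plan follows.
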